**Table 3 Group 2: Schedule of Events**

	Screen	BL	Treatment Phase				ET	Safety Follow-up
Visit	1	2	3	4	5	6	7	
Day End of Week	Days -31 to -3	Day -1	Day 7 (±1) Week 1	Day 14 (±1) Week 2	Day 21 (±1) Week 3	Day 28 (±1) Week 4	Day 35 (±1) Week 5	
Clinic visit	X	X	X	X	X	X	X	
Informed Consent	X							
Demographics	X							
ESS	X	X	X	X	X	X	X	
Berlin Sleep Apnea Questionnaire	X							
UK PDS Brain Bank Criteria	X							
MDS-UPDRS Parts III and IV a (on-state)		X	X	X	X	X		
CGIs		X						
CGIc			X	X	X	X		
Medical History	X							
Prior and Concomitant Medications and Therapies	X	X b	X b	X b	X b	X b	X	
Physical Examination	X	X	X	X	X	X	X	
Height	X							
Weight	X	X	X	X	X	X	X	
Calculate BMI	X							
Vital Signs c	X	X	X	X	X	X	X	
QUIP-RS	X							
BDI-2	X							
C-SSRS	X	X	X	X	X	X	X	
12-Lead ECG	X	X	X	X	X	X	X	
Safety Laboratory Tests d	X	X e	X	X	X	X	X	
Urinalysis	X	X e	X	X	X	X	X	
Serum Pregnancy Test f	X							
Urine Pregnancy Test f		X	X	X	X	X	X	
Urine Drug Screen	X							
Alcohol Breath Test	X	X	X	X	X	X	X	
Study Drug Administration			X	X	X	X		
Light Breakfast and/or Lunch g	X	X	X	X	X	X	X	
PGIc			X	X	X	X		
FSS		X	X	X	X	X		
Apathy Scale		X	X	X	X	X		
SCOPA-cog	X	X	X	X	X	X		

[figure not shown]

	Screen	BL	Treatment Phase				ET	Safety Follow-up
Visit	1	2	3	4	5	6	7	
Day End of Week	Days -31 to -3	Day -1	Day 7 (±1) Week 1	Day 14 (±1) Week 2	Day 21 (±1) Week 3	Day 28 (±1) Week 4	Day 35 (±1) Week 5	
Adverse Event Assessment	X	X	X	X	X	X	X	
Review I/E Criteria	X	X						
Randomization		X						
Dispense Study Drug		X	X	X	X			
Drug Accountability			X	X	X	X	X	

BDI-2 = Beck Depression Inventory-2; BL = Baseline; BMI = body mass index; CGIc = Clinical Global Impression of Change; CGIs = Clinical Global Impression of Severity; C-SSRS = Columbia-Suicide Severity Rating Scale; ECG = electrocardiogram; ESS = Epworth Sleepiness Scale; ET = Early Termination; FSS = Fatigue Severity Scale; I/E = inclusion/exclusion; MDS-UPDRS = Movement Disorders Society-Unified Parkinson’s Disease Rating Scale; PDS = Parkinson’s Disease Society; PGIC = Patient Global Impression of Change; QUIP-RS = Questionnaire for Impulsive-Compulsive Disorders in Parkinson’s disease Rating Scale; SCOPA-cog = Scales for Outcomes in Parkinson’s disease-cognition; UK = United Kingdom

- a The Hoehn and Yahr stage is assessed in Part III of the MDS-UPDRS.
- b Review concomitant medications to verify PD medications, sleep medications allowed by the protocol, and when applicable, study drug (as specified in Section 5.3 of the protocol) were taken appropriately. For subjects currently receiving treatment for OSA, review OSA therapy device usage to ensure adequate compliance.
- c At the Baseline visit, vital signs (body temperature, respiratory rate, blood pressure [seated and standing], and pulse [seated and standing]) will be taken as soon as possible upon arrival at the study center. Additional blood pressure [seated and standing], and pulse [seated and standing] measurements will be taken at approximately 2 and 3 hours after the first set of vital signs (see Section 7.2 of the protocol for details). On Treatment Visits 3, 4, 5, and 6, vital signs (body temperature, respiratory rate, blood pressure [seated and standing], and pulse [seated and standing]) will be taken approximately 1 hour prior to dosing at the clinic. Additional blood pressure [seated and standing], and pulse [seated and standing] measurements will be taken at approximately 1 and 2 hours after dosing (see Section 7.2.2 of the protocol for details). On Safety Follow-up, vital signs (body temperature, respiratory rate, blood pressure [seated and standing], and pulse [seated and standing]) will also be taken.
- d Additional safety laboratory samples may be obtained at the investigator’s discretion.
- e If the Baseline visit occurs outside of the screening window (i.e., >29 days after the Screening visit) obtain blood samples for serum chemistry, hematology and a urine sample for urinalysis.
- f Subjects who are not of childbearing potential (i.e., postmenopausal, surgically sterile, or who have medically documented ovarian failure will not need to undergo pregnancy testing).
- g At the Screening and ET visits, subjects may be provided a light breakfast as described in Sections 7.1 and 7.5 of the protocol, respectively. At Baseline and at Visits 3, 4, 5, and 6, subjects may be provided a light breakfast as described in Section 7.2.2 of the protocol.

### **3.6. CHANGES TO ANALYSIS FROM PROTOCOL**

Changes to planned analysis from protocol are:

- The modified Intent-to-Treat (mITT) analysis population is now defined as all randomized subjects who received at least one dose of study drug and have a Baseline and at least one post-Baseline efficacy assessment (refer to Section 5.2) while it was defined as follows in the protocol: all subjects who were randomized, received at least one dose of study medication and have baseline and at least one post-baseline evaluation of ESS;
- When computing the ESS total score, missing ESS item(s) will be imputed by the mean of the non-missing items only if only one or two ESS items are missing. Should three items or more be missing, the ESS total score will not be computed (refer to Section 16.1.1);
- Similarly, imputation techniques for missing MDS-UPDRS Part III individual scores when computing the MDS-UPDRS Part III total score are now planned to be done (refer to Section 16.2.1.2);
- The main analysis of each efficacy endpoint will be done based on the mITT population instead of the efficacy (EFF) population. Sensitivity analysis will be performed based on the EFF;
- Period will be used in the main model instead of the treatment-by-sequence interaction;
- Summaries by sequence will not be presented for the vital signs and electrocardiogram (ECG) endpoints, with the exception of the placebo treatment group for which summaries further broken down by sequence will be presented;
- No subgroup analyses will be conducted by disease severity, treatment with levodopa and treatment with a combination of dopamine agonists and levodopa;
- Non-compartmental PK analysis will be based on multiple dosing as described in Section 18.3
- Numbers and percentage of subjects with abnormal laboratory values post-baseline will not be tabulated by treatment group; only a listing of subjects with abnormal laboratory values will be provided

[figure not shown]

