	
endpoint-based power calculations were performed for reference. A sample size of 34 subjects (assuming 17 completing in each of the Sequences A and B) will provide 80% power to detect a difference of 3 points in the change from baseline in ESS score between one of the JZP-110 and placebo groups not adjusting for multiple comparisons. This calculation assumes a common standard deviation (SD) of 6 points for the change from baseline in ESS score and a 2-sided significance level of 0.05 using an analysis of variance (ANOVA)-based t-test for difference of means in a crossover design.
 
The rationale for including Sequence C in the study is to preserve study blinding.
 
Statistical Analysis
 
Safety and tolerability of JZP-110 is the primary objective of this study and descriptive statistics of all safety endpoints will be presented by treatment. No inferential statistics will be provided for safety endpoints.
 
For the analysis of the key efficacy endpoint of change from baseline in ESS, a mixed-effects model will be used as the primary method of analysis. This model will include fixed effects for treatment (dose), sequence, treatment-by-sequence interaction, and baseline value of the efficacy endpoint. The model will also include a random effect for subject within sequence. Model-adjusted differences between each active treatment dose (75, 150, and 300 mg) and placebo, along with 95% confidence intervals, will be presented.
 
For the analysis of the MWT exploratory endpoint, a similar mixed-effects model as for ESS will be used. However, because the MWT will be optional and consequently result in a reduced sample size, there may be convergence issues associated with the mixed-effects model. In the event such issues do arise, an analysis of covariance (ANCOVA) model without accounting for treatment sequence may be used at each visit.
 
For the analysis of the efficacy endpoints of improvement in PGIC and CGIC scores, chi-square tests will be used to test hypotheses of differences between placebo and each active dose. A mixed-effects model similar to the model described above will be used for the analysis of MDS-UPDRS, FSS, Apathy Scale, and SCOPA-cog endpoints. No adjustment for multiple testing will be performed.
 
Summary statistics for all efficacy assessments will be

--	--

JZP-110

Clinical Trial Protocol: JZP166-201 Amendment 2

Jazz Pharmaceuticals

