## **9.8 Primary Objective**

The primary objective of this study is the safety and tolerability of JZP-110 administered to subjects with excessive sleepiness and PD. This will be assessed by the occurrence of and/or clinically significant changes in:

- Treatment-emergent AEs
- Discontinuations due to AEs
- Clinical laboratory tests (chemistry, hematology, and urinalysis)
- Vital signs
- 12-lead ECGs
- Physical examination
- C-SSRS

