### 9.13.3 Laboratory Evaluation

The number and percent of subjects with abnormal values post-baseline will be tabulated by treatment. In addition, summary statistics (i.e., mean, minimum, maximum, SD, and number of subjects) will be presented by treatment/dose group for each laboratory. An additional listing of subjects with clinically significant laboratory values will be generated. Detailed laboratory value analyses, and the algorithms to derive variables for the clinically significant changes will be specified in the Statistical Analysis Plan.

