## **17.2. LABORATORY EVALUATIONS**

[figure not shown]
Laboratory results will be reported in SI Units.

The following summaries will be provided based on the SAF for the hematology, serum chemistry, and urinalysis data (refer to APPENDIX 3 for the list of laboratory parameters to be included in the summaries):

- Observed and change from Baseline by visit for quantitative (continuous) measurements
- Observed by visit for qualitative (categorical) measurements

A listing of subjects with abnormal value(s) according to normal range criteria (refer to 17.2.1) will be provided.

All laboratory results, including pregnancy test, urine drug screen, and alcohol breath test, will be presented in subject data listings.

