### 17.2.1. LABORATORY STANDARD REFERENCE RANGES AND MARKEDLY ABNORMAL CRITERIA

Quantitative laboratory measurements will be compared with the relevant laboratory reference ranges in SI units and categorized as:

- Low: result < LLN
- Normal: result within the laboratory normal reference range (upper and lower limit included)
- High: result > ULN

[figure not shown]

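### The SAP withdraws the by-treatment count of subjects with abnormal laboratory values, so no planned table gives that count by dose for the quantitative tests

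*SAP*

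**What the plan says.** Protocol 9.8 lists what the primary objective will be judged on. One item, separate from adverse events, begins "Clinical laboratory tests (chemistry, hematology, and urinalysis". The protocol synopsis adds that "descriptive statistics of all safety endpoints will be presented by treatment", and Protocol 9.13.3 is specific for the laboratory: "The number and percent of subjects with abnormal values post-baseline will be tabulated by treatment".

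SAP 3.6 changes this. The counts "will not be tabulated by treatment group; only a listing of subjects with abnormal laboratory values will be provided". No reason is given. The change is current analysis text, because SAP 17.2 matches it. That section plans three outputs. The numeric tests get a summary of results and of their change since baseline at each visit. The categorical tests get a summary of results at each visit. For out-of-range results the plan is: "A listing of subjects with abnormal value(s) according to normal range criteria (refer to 17.2.1) will be provided".

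SAP 17.2.1 nevertheless keeps the classification: "Quantitative laboratory measurements will be compared with the relevant laboratory reference ranges in SI units and categorized as" Low, Normal or High against the reference limits.

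**The concern.** The classification is derived and then feeds only a listing. ECG (SAP 17.3) keeps incidence and shift tables, and so do seated blood pressure and pulse rate (SAP 17.4.2). The quantitative laboratory tests have neither.

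Laboratory harm often shows as a few subjects with large changes rather than as a shift of the average. In an ascending-dose study whose primary objective is safety, the natural display is how many subjects became abnormal at placebo, 75, 150 and 300 mg, out of how many measured. Without it, a reader of the report has to assemble that comparison by hand for each test.

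**Working it through.** The plan states no figure to reproduce. The check compares the planned outputs and then asks what the missing table would show.

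**Step 1: what each remaining output gives for a quantitative test.**

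- *Continuous summaries* (SAP 17.2, with the statistics in SAP 6 and the by-treatment default in SAP 17) give n, mean, SD, median, minimum and maximum. They show that an extreme exists, but not how many subjects were out of range or whether they were so at entry.
- *Qualitative summaries* (SAP 17.2) give frequencies, but only for categorical results such as dipstick urinalysis. They do not cover hematology, chemistry or the numeric urinalysis tests.
- *The abnormal-value listing* shows the dose at each assessment (SAP 6). It covers abnormal subjects only, so it carries no denominators.
- *Adverse event tables* (SAP 17.1) count laboratory changes by treatment when the investigator judges them clinically significant (Protocol 6.14.1), and the liver-enzyme events that Protocol 6.14.1.4 defines numerically.

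None of the four gives n/N out of range by dose relative to baseline.

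**Step 2: planned denominators.** SAP 3.4 expects 21:21:7 in Sequences A, B and C. Each active dose is planned for A and B: 21 + 21 = 42. Placebo is given in all three: 21 + 21 + 7 = 49. Both are before dropout.

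**Step 3: an illustration with assumed values.** Suppose 2 of 42 subjects on 300 mg have an ALT rise of 80 U/L and the other 40 do not change.

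- Mean change: 2 × 80 / 42 = 3.8 U/L.
- Contribution to the SD: 80 × √[(2/42) × (40/42)] = 17.0 U/L.
- Maximum change: 80 U/L.
- Incidence: 2/42 = 4.8%, exact 95% interval 0.6% to 16.2%.

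The mean hides the two subjects. The SD and maximum hint at them. Only the count says that there are two.

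**Step 4: how informative the count would be.** With zero cases the exact two-sided 95% upper limit is 1 − 0.025^(1/N): 8.4% for N = 42 and 7.3% for N = 49. The chance of seeing at least one case in 42 is 1 − (1 − p)^42: 57%, 88% and 99% for assumed true rates of 2%, 5% and 10%.

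**Step 5: comparability of the extremes.** SAP 17 averages a Sequence C subject's end-of-period values for descriptive statistics. If this is applied to the laboratory summaries, one result 80 U/L above three otherwise equal results enters as 80 / 4 = 20 U/L. That affects up to 7 of the 49 placebo subjects and no active-dose subject, so the maximum on placebo is not quite like the maximum on an active dose. The SAP 17 rules for incidences (count once) and shifts (worst value) avoid this dilution.

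**The case against.** The case for leaving the plan alone has several sound parts.

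- *More than means remain.* A reader might infer from SAP 3.6 that only averages are left. That is wrong: the same summaries carry SD, median, minimum and maximum, and in the illustration they would flag the outliers.
- *The comparison can be recovered.* A reader might infer that laboratory safety cannot be assessed by dose. The documents do not support that. The listing shows dose, the summaries give n, and all laboratory results are listed. A count by dose can be built by hand.
- *Some incidences are tabulated.* Qualitative tests keep frequencies. Clinically significant changes and the numeric liver-enzyme events reach the adverse event tables, and events leading to discontinuation are tabulated separately.
- *The change is disclosed.* SAP 3.6 declares it before database lock and unblinding. It is neither hidden nor a contradiction within the SAP. Safety has no inferential analysis, so no estimate or error rate moves.
- *A raw count would be blunt.* Exclusion 17 removes only values judged clinically significant, so subjects may enter with out-of-range results. A simple post-baseline count would include them at every dose.

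All of this stands as a limit on the point. It does not remove the point. Recovery by hand is not a planned output, and the adverse event route depends largely on investigator judgement and covers only the more marked changes. The last objection concerns the form of the table and is met by using baseline status. The protocol did not promise a laboratory shift table, so that form is a recommendation that goes beyond restoring the protocol's plan.

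**Conclusion.** The point holds in a limited form. For quantitative hematology, chemistry and urinalysis tests, a table promised in the protocol for a named component of the primary objective has been dropped without a stated reason, and nothing planned replaces it directly. It is a gap in the descriptive safety display. It does not leave the laboratory question unanswerable, and it has no effect on any test.

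What is lost is n/N by dose on about 42 subjects per active dose and 49 on placebo: enough to show an emergent abnormality at a true rate of 5% at least once with 88% probability, but too few for precise rates. These figures assume the planned allocation and no dropout. The ALT values and true rates are assumed. The table shells that SAP 8 mentions were not available, and the conclusion takes SAP 3.6 and 17.2 as governing them.

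**What to change.** In SAP 17.2, restore for each quantitative test the n/N (%) of subjects with Low and with High post-baseline values, for each dose, pooled JZP-110 and placebo. Use as denominator the number of subjects with a value at that dose. Present it as a baseline to post-baseline shift table, or restrict it to subjects normal at baseline, so that abnormalities present at entry are not counted as emergent. Apply the SAP 17 rules already written for Sequence C and the pooled group. Keep the listing and delete the SAP 3.6 bullet.

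The cost is one or two descriptive tables built from categories already derived, with no new data. One reading note should go with them. Doses ascend in both active sequences (75 mg in Periods 1 and 2, 150 mg in Periods 2 and 3, 300 mg in Periods 3 and 4), so counts by dose are partly counts by time on study and should be read with period in mind. Sequence C also has four periods in which to contribute a placebo abnormality, whereas Sequences A and B have one each. A breakdown of placebo by sequence, which SAP 17 already provides for, would show this.

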## **4. PLANNED ANALYSES**

[figure not shown]
### **4.1. DATA MONITORING COMMITTEE**

There will be no data monitoring committee (DMC) for this study.

[figure not shown]
### **4.2. INTERIM ANALYSIS**

There will be no interim analysis (IA) for this study.

### **4.3. FINAL ANALYSIS**

All final, planned analyses identified in this SAP will be performed by  following sponsor approval of this SAP, sponsor approval of the list of protocol deviations that define the per protocol (PP) and PK analysis populations, database lock (DBL), and unblinding of the study.

## **5. ANALYSIS POPULATIONS**

### **5.1. ALL RANDOMIZED SUBJECTS POPULATION**

The all-randomized subjects population (RND) will include subjects who signed the informed consent form and who were randomized. This analysis population will be used to summarize subject disposition overall and by sequence and period. This analysis population will also be used to summarize protocol deviations and inclusion/exclusion from the analysis populations, including reasons for exclusion from each analysis population overall and by sequence.

### **5.2. MODIFIED INTENT-TO-TREAT POPULATION**

[figure not shown]
The modified intent-to-treat population (mITT) will contain all randomized subjects who received at least one dose of study drug and have a Baseline and at least one post-Baseline efficacy assessment. This analysis population will be used to perform the primary analysis of the key and exploratory efficacy endpoints (refer to Sections 16.1.4 and 16.2.3, respectively). It will also be used to summarize subjects' demographic and other Baseline characteristics, exposure to study drug, and treatment compliance data. For summaries and analyses presented based on the mITT, subjects will be classified according to randomized treatment group. If a subject in the mITT population has missing data on a specific endpoint that would require exclusion from an analysis, that subject will be excluded in the analysis of that endpoint only.

### **5.3. EFFICACY POPULATION**

The efficacy population (EFF) will contain all subjects in the mITT from Sequences A and B. This analysis population will be used to perform a sensitivity analysis for the key efficacy endpoint (refer to Section 16.1.5). For summary and analysis presented based on the EFF, subjects will be classified according to randomized treatment group. If a subject in the EFF population has missing data on a specific endpoint that would require exclusion from an analysis, that subject will be excluded in the analysis of that endpoint only.

### **5.4. PER PROTOCOL POPULATION**

The per-protocol population (PP) will contain all subjects from the mITT, where subjects with major

deviations having an impact on efficacy endpoint(s) will be assessed, flagged, and excluded from this analysis population. The final list of major protocol deviations resulting in exclusion of subjects from the PP will be determined and approved by the sponsor prior to DBL.

Major protocol deviations resulting in exclusion of subjects from the PP may include, but are not limited to:

- Subjects not meeting the key entry inclusion/exclusion criteria
- Subjects who received the wrong treatment during a period
- Subjects with major protocol deviation(s) related to prohibited medications
- Subjects with major protocol deviation(s) related to study drug non-compliance

This analysis population will be used to perform sensitivity analyses for the key efficacy endpoint (refer to Section 16.1.5) and exploratory efficacy endpoint (refer to Section 16.2.4).

## **5.5. SAFETY POPULATION**

The safety population (SAF) will include all subjects who took at least one dose of study drug. This analysis population will be used to summarize subjects' demographic and other Baseline characteristics, disease history, medical/surgical history, concomitant medications, exposure to study drug, treatment compliance, and safety data. For summaries presented based on the SAF, subjects will be classified according to the treatment received.

## **5.6. PHARMACOKINETIC POPULATION**

The PK population will consist of all subjects who enrolled under the Original Protocol or Amendment 1 and received study drug and provided post-dose PK data for at least 1 timepoint. Subjects with protocol violations or events with potential to affect the PK concentrations will be evaluated on a case by case basis.

## **6. GENERAL CONSIDERATIONS**

[figure not shown]
Categorical variables will be reported as frequency and percent. Continuous variables will be reported as number of subjects with available data (n), mean, SD, median, minimum, and maximum.

Listings will include the group number (e.g., Group 1 or Group 2) in which a subject was enrolled, the treatment sequence to which he/she was randomized, and the dose the subject received at the time of each assessment.

